5.2. Determination of Sample Size

5.2.1. Clinical Protocol RHCD

Sample size of this study is based on the regulatory requirements from the European Medicine's Agency Paediatric Investigation Plan for ixekizumab. The regulatory requirements for the number of subjects in each treatment group were: (1) at least 170 randomized subjects (at least 90 to ixekizumab, at least 25 to etanercept, and at least 55 to placebo); and (2) at least 30% of subjects from the EU.

In the main protocol RHCD, approximately 165 subjects will be randomized in a 2:1 ratio to receive ixekizumab (110 subjects) or placebo (55 subjects) during the Double-Blind Treatment Period. The study will have >99% power to test the superiority of ixekizumab to placebo for PASI 75 and for sPGA (0,1) at Week 12, based on the 2-sided Fisher's exact test at a significance level of 0.05. The following assumptions were used for the power calculations for both sPGA (0,1) and PASI 75 responses rates, based on ixekizumab clinical studies in adult subjects with moderate-to-severe Ps efficacy data (Griffiths et al. 2015; Gordon et al. 2016): 80% response for ixekizumab and 10% response for placebo for both PASI 75 and sPGA (0,1).

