6.14.2. Adverse Events

Adverse events will be classified based upon the latest version of the MedDRA. Adverse events will be recorded at every study visit. Any condition starting on or after the date of informed consent will be considered an AE. Any preexisting condition which worsens in severity on or after the date of informed consent will be considered and recorded as an AE on the Adverse Event (AE) eCRF page from the date of worsening onward.

A treatment-emergent adverse event (TEAE) is defined as an event that first occurred or worsened in severity after baseline and on or prior to the date of the last visit within the defined treatment period. Both the date/time of the event and the date/time of the dose (that is, injection) are considered when determining TEAEs. Treatment-emergent AEs will be assigned to the study period to which it is considered treatment-emergent:

- The MedDRA lowest level term (LLT) will be used when classifying AEs as treatment-emergent.
- The maximum severity recorded for each LLT prior to the first dose date/time in the treatment period will be used as the pre-treatment severity for that LLT. If an event during the baseline period has missing severity, and the event persists during the treatment period, then it will be considered as treatment-emergent, regardless of the postbaseline level of severity. Events with a missing severity during the treatment period will be considered treatment-emergent.
- AEs with a particular LLT will be classified as treatment-emergent if they first start on or after the first dose date/time in the treatment period (that is, a patient has no preexisting conditions with that LLT), or if the severity is greater than the pre-treatment severity for that LLT. If a partial AE start date/time is present, the date/time will be compared as far as possible to the treatment start date/time in order to determine whether the event is treatment-emergent. If there is any doubt, the event will be flagged as treatment-emergent.

A follow-up-emergent adverse event (FEAE) is defined as an event that first occurred or worsened in severity after the date of Visit 31 (that is, Week 108) or the ETV:

- The MedDRA LLT will be used when classifying AEs as follow-up-emergent.
- For AEs that are ongoing at the date of Visit 31 or ETV, the maximum severity recorded for each LLT on or prior to the date of Visit 31 or ETV will be used as the follow-up baseline severity for that LLT.

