6.14.3. Deaths, Other Serious Adverse Events, and Other Notable Adverse Events

By-patient listings of deaths, SAEs, and AEs leading to discontinuation will be provided, respectively.

All deaths will be included, regardless of the investigator's or the Sponsor's judgment about causality, including:

- any deaths occurring during participation in the study in the database for which data are being presented
- any deaths occurring after a patient leaves (is discontinued from or completed) the study in the database for which data are being presented if the death is:
 - the result of a process initiated during the study, regardless of when it actually occurred
 - occurs during the Period 5 after discontinuation of study drug

An SAE is any AE that results in one of the following outcomes: death, life-threatening, initial or prolonged hospitalization, disability or permanent damage, congenital anomaly or birth defect, or any other serious/important medical events.

The following summary tables (including treatment group comparison for Period 2) will be provided for P2 Main Study Safety Population and All Ixekizumab Safety Population:

- SAEs by SOC and PT
- AEs that lead to treatment discontinuation (including death) by SOC and PT

The following summary tables (including treatment group comparisons for Period 2 and Period 4) will be provided P2 Addendum Safety Population and P4 Randomized Withdrawal Population:

- SAEs by SOC and PT

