6.16. Protocol Deviations

Protocol deviations will be identified throughout the study. Important protocol deviations are defined as those deviations from the protocol likely to have a significant impact on the completeness, accuracy, and/or reliability of the study data, or that may significantly affect subject's rights, safety, or well-being.

The major protocol deviations, which are the subset of the important protocol deviations, are the protocol deviations that might have impact on the efficacy and/or safety results. The impact of major protocol deviations on the efficacy results will be investigated by assessing the robustness of the study results and conclusions to the choice of analysis population, both by including and excluding the data potentially affected by major protocol deviations. As specified in Section 6.1.1, the PPS Population is defined as all randomized patients who do not have major protocol deviations.

Table RHCD.6.12 includes the categories and subcategories of important protocol deviations, whether or not these deviations are major protocol violations, the action to be taken regarding the exclusion of patients from PPS, the source of the deviation identified, and the statistical programming guidance for the clinical study report (CSR).

The number and percentage of patients having important protocol deviation(s) will be summarized within category and subcategory of deviations by treatment group for the ITT Population for the Double-Blind Treatment Period (Period 2).

A by-patient listing of important protocol deviations will be provided.

Table RHCD.6.12. Identification and Action of Important Protocol Deviations

Important Protocol Deviation Category/Subcategory/Study Specific	Action for PPS Analysis	Source to Identify Protocol Deviation ^a	Statistical Programming Guidance for Clinical Study Report
Category: Eligibility			
Subcategory: Inclusion/Exclusion			
[1] No confirmed diagnosis of moderate-to-severe plaque-type Ps for at least 6 months prior to Visit 2	Excluded from PPS	Monitor and Stats	Either from monitor’s list, or, if date of diagnosis of Ps is missing or less than 6 months prior to Visit 2.
[2] PASI score <12 or sPGA <3 or BSA involvement <10% at Visit 1 or Visit 2	Excluded from PPS	Monitor and Stats	Either from monitor’s list, or, If PASI score <12 or sPGA <3 or BSA involvement <10% or any missing at Visit 1 or Visit 2.

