[D8] Neutrophil counts <500 cells/μL, or ≥500 and <1000 cells/μL based on 2 test results, or ≥1000 and <1500 cells/μL based on 3 test results and a concurrent infection	Do not exclude from PPS	Monitor and Stats	Either from monitor’s list, or, If a patient still receives study treatment after 10 days with confirmed segmented neutrophil counts <500 cells/μL (defined as a test of <500 cells/μL and a retest within 10 days still <500 cells/μL; if no retest, use the test as the confirmed).
[D9] Total WBC count <2000 cells/μL	Do not exclude from PPS	Monitor and Stats	Either from monitor’s list, or, If a patient still receives study treatment after 10 days with confirmed total WBC count <2000 cells/ μL (defined as a test of <2000 cells/μL and a retest within 10 days still <2000 cells/μL; if no retest, use the test as the confirmed)
[D10] Lymphocyte count <200 cells/μL	Do not exclude from PPS	Monitor and Stats	Either from monitor’s list, or, If a patient still receives study treatment after 10 days with confirmed lymphocyte count <200 cells/μL (defined as a test of <200 cells/μL and a retest within 10 days still <200 cells/μL; if no retest, use the test as the confirmed).

Important Protocol Deviation Category/Subcategory/Study Specific	Action for PPS Analysis	Source to Identify Protocol Deviation^a	Statistical Programming Guidance for Clinical Study Report
[D11] Platelet count <50,000 cells/ μ L	Do not exclude from PPS	Monitor and Stats	Either from monitor’s list, or, If a patient still receives study treatment after 10 days with confirmed platelet count <50,000 cells/ μ L (defined as a test of <50,000 cells/ μ L and a retest within 10 days still <50,000 cells/ μ L; if no retest, use the test as the confirmed).
[D12] Subject BP readings are greater than 95 th percentile at 3 consecutive study visits	Do not exclude from PPS	Monitor	From monitor’s list.
[D13] A severe AE or an SAE, or a clinically significant change in a laboratory value	Do not exclude from PPS	Monitor and Stats	Either from monitor’s list, or, If patient still receives study treatment on the same day or after the date with an AE or SAE.
[D14] Clinically significant systemic hypersensitivity reaction that does not respond to treatment	Do not exclude from PPS	Monitor	From monitor’s list.
[D15] Patient became pregnant	Do not exclude from PPS	Monitor	From monitor’s list.
[D16] Patient developed a malignancy (more than 2 nonmelanoma skin cancers)	Do not exclude from PPS	Monitor	From monitor’s list.

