The term “Stats” indicates the protocol deviation will be programmed based on data in clinical database by statistical programmers with the statistical programming guidance provided as the last column. The detailed programming specification will be documented in Analysis Data Model (ADaM) specification.

The terms “Monitor and Stats” indicates the protocol deviation will be a combination of monitor’s list (SDTM.DV domain) and statistical programming from clinical database, the deviation will show if either source identifies.

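### Deviation D13 drops the word severe from its programming guidance, so coded as written it flags continued dosing after any adverse event (wrong as written, minor)

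*SAP*

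**What the plan says.** D13 sits in Table RHCD.6.12 (SAP Section 6.16), in the subcategory for subjects kept on treatment despite meeting a discontinuation criterion. Its label is: "A severe AE or an SAE, or a clinically significant change in a laboratory value". The source is given as monitor and statistics jointly, and the per-protocol action is not to exclude. The guidance column adds to the monitor's list this programmed condition: "If patient still receives study treatment on the same day or after the date with an AE or SAE".

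Footnote a to the table says how the columns are used. Deviations from the statistics source are coded from the clinical database "by statistical programmers with the statistical programming guidance provided as the last column". Where both sources apply, "the deviation will show if either source identifies". The same footnote places the detailed specification in the ADaM document.

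Section 6.16 sets out the reporting: "The number and percentage of patients having important protocol deviation(s) will be summarized within category and subcategory of deviations by treatment group". This is for the ITT Population in Period 2, and a by-patient listing is also planned.

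**The concern.** The label and the guidance in one row describe different sets of subjects. The label reaches those who continue after an event serious or severe enough to call for stopping. The guidance, taken at its word, reaches anyone dosed on or after the date of any AE.

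Section 6.16 reserves important deviations for departures likely to affect the data materially, or the subject's rights, safety or well-being. Continuing treatment through a mild, non-serious event is ordinary conduct and does not fit that description. If it is flagged, the discontinuation-criteria line in the deviation table is too high in every arm where such events occur. In a paediatric trial a reader could take the line as evidence that sites ignored stopping rules. The genuine cases would also be hard to find in the listing.

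**Working it through.** The plan gives no figure to reproduce, so the check is a comparison of texts.

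1. **Label against guidance.** The label has three limbs: severe AE, SAE, clinically significant laboratory change. The guidance has two: AE, SAE. The severity qualifier is gone from the first limb, and the laboratory limb has no programmed counterpart.

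2. **What AE means here.** Section 6.14.2 counts as an AE any condition starting on or after informed consent, with no severity threshold. Section 6.14.3 begins its definition "An SAE is any AE that results in one of the following outcomes", so SAEs are a subset of AEs. An AE or an SAE therefore reduces to any AE.

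3. **Which column governs the code.** Footnote a points programmers to the last column. The neighbouring rows D1 to D5, D7 and D9 to D11 repeat their limits in that column, so leaving the limit to the label is not the table's usual practice.

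4. **Whether anything restores the limit.** No other place in the SAP or the protocol addendum limits the D13 rule to severe events.

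5. **Whether the monitor can correct it.** With two sources joined by *or*, the flagged set is the union of the monitor's list and the programmed set. A union can only add subjects, so a programmed flag stands even if the monitor recorded nothing.

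6. **Where the flag goes.** It enters the by-arm count and percentage and the listing. It does not enter the per-protocol set, because the D13 action is not to exclude.

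7. **Size.** The excess in an arm is x × n. Here n is the arm size (planned 110 ixekizumab and 55 placebo, SAP Section 5.2.1). x is the share of that arm dosed on or after the date of a mild or moderate non-serious AE, with no other flag in the subcategory. The documents give n but neither an AE rate nor a split by severity, so x is unknown and the product cannot be evaluated.

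**The case against.** The strongest reply is that the guidance is shorthand. It sits beside its own label, and on the literal reading the words about SAEs are redundant, whereas as an abbreviation of the label they are not. The column is loose elsewhere too: D6 is labelled at 2.5 times ULN for ALP but confirmed at 3 times, and D8 programs only the branch below 500 cells/μL. Operational detail is also assigned to the ADaM specification. This stands as a reason to doubt that the miscount will occur. It does not make the text right. A column that departs from its labels in other rows is a poor basis for assuming that it follows the label here.

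Three stronger readings are tempting, and the documents support none of them.

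- **A large or quantified inflation.** A reader might put an AE rate into step 7 and report a count out of 165. No rate is given, so any such count would reflect only the rate chosen.
- **A threat to the efficacy or safety conclusions.** D13 leaves the per-protocol set unchanged. The ITT, co-primary and AE analyses do not use the flag.
- **A count that measures AE frequency instead of failures to stop.** The corrected rule would also vary with each arm's rate of severe and serious events. The difference is one of degree.

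**Conclusion.** Wrong as written, and minor. The mismatch between label and guidance is certain from the text. That it produces a wrong count is conditional on the guidance being coded literally, which cannot be settled without the ADaM specification. The main protocol's discontinuation criteria are not supplied either, so D13's own label is the reference for what was intended.

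If coded literally, the discontinuation-criteria count is too high wherever an arm has subjects who were dosed after a mild or moderate non-serious AE and have no other flag in that subcategory. The amount is not derivable. The consequence ends at the important-deviation summary and the by-patient listing.

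**What to change.** Insert the word severe before AE in the D13 guidance, so that the programmed trigger is a dose on the same day as, or after the date of, a severe AE or an SAE. Change nothing else in the cell. Leave clinically significant laboratory changes to the monitor's list and to rules D1 to D11, which already cover hepatic and haematology thresholds.

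Do not add a test that the dose came after event onset on the same day. Section 6.14.2 does use times for another purpose ("Both the date/time of the event and the date/time of the dose (that is, injection) are considered when determining TEAEs"), but it also imputes a missing AE start time as 23:59. Under an onset-time test, a severe AE with unknown start time would be placed after that day's injection, and a same-day violation would go unflagged. The existing same-day wording catches it.

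The cost is one word in the SAP and a matching check of the ADaM specification. Severity and seriousness already feed the AE tables in Sections 6.14.2 and 6.14.3. The SAP's revision history places Version 3 after the 12-week database lock, so any Period 2 deviation table already produced should be checked against the corrected rule.

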Intent-to-Treat (ITT) – Etanercept Approved Countries (per Protocol Addendum[2])	Double-Blind Treatment Period (Period 2)	All randomized subjects per Protocol Addendum(2) in etanercept-approved countries (that is, subjects with severe psoriasis in countries where etanercept is used as a reference arm), even if the subject does not take the assigned treatment, does not receive the correct treatment, or, otherwise, does not follow the protocol. Subjects will be analyzed according to the treatment to which they were assigned.
Per-Protocol Set (per main study)	Double-Blind Treatment Period (Period 2)	All randomized subjects who do not have significant protocol violations (refer to Section 6.16). Subjects will be analyzed according to the treatment to which they were assigned. .
Safety Population (per main study)	Double-Blind Treatment Period (Period 2)	All randomized subjects who take at least 1 dose of double-blind study treatment. Subjects will be analyzed according to the treatment to which they were assigned.

Population	Period	Description
Safety Population – Etanercept-Approved Countries (per Protocol Addendum[2])	Double-Blind Treatment Period (Period 2) per Protocol Addendum(2)	All randomized subjects in Protocol Addendum(2) in etanercept countries who take at least 1 dose of double-blind study treatment per Protocol Addendum(2). Subjects will be analyzed according to the treatment to which they were assigned.
Double-Blind, Randomized Withdrawal Period Population	Randomized-Withdrawal Period (Period 4) per Protocol Addendum(2)	All re-randomized patients (that is, subjects from countries in the EU who were re-randomized at Week 60) who received at least 1 dose of study treatment during Double-Blind, Randomized Withdrawal Period.
Ixekizumab Efficacy Primary Population	Combined Treatment Periods (Periods 2, 3, and 4)	All subjects randomized to ixekizumab at Week 0 (Visit 2) and who received ixekizumab throughout their study participations. The following subjects are not included in this analysis population: (1) patients randomized to etanercept or placebo at Week 0; and (2) patients who are re-randomized to placebo during Period 4 per Protocol Addendum(2).

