Missing CDRS-R total score: missing baseline or any scheduled visit prior to discontinuation visit	Do not exclude from PPS	Stats	If missing CDRS-R total score baseline or any scheduled visit prior to discontinuation visit.
Missing C-SSRS: missing baseline or any scheduled visit prior to discontinuation visit	Do not exclude from PPS	Stats	If missing C-SSRS baseline or any scheduled visit prior to discontinuation visit. C-SSRS is missing if the whole questionnaire is missing.

Important Protocol Deviation Category/Subcategory/Study Specific	Action for PPS Analysis	Source to Identify Protocol Deviation^a	Statistical Programming Guidance for Clinical Study Report
Missing sPGA: not having Week 12 measurement for patients who have completed Week 12	Do not exclude from PPS. Note: such patients will be treated as nonresponders at Week 12	Stats	If not having Week 12 sPGA measurement for patient who have completed week 12.
Missing PASI: not having Week 12 measurement for patients who have completed Week 12	Do not exclude from PPS. Note: such patients will be treated as nonresponders at Week 12	Stats	If not having Week 12 PASI measurement for patient who have completed week 12.
Had unqualified site personnel perform clinical safety and/or efficacy assessments	Do not exclude from PPS	Monitor	From monitor's list.
Missing parents/other adult to respond CDRS-R scale at any visit	Do not exclude from PPS	Monitor	From monitor's list.
Missing or Unqualified blinded assessor	Do not exclude from PPS	Monitor	From monitor's list.
Category: Investigational Product			
Subcategory: Treatment Assignment/Randomization Error			
Took incorrect study medication	Do not exclude from PPS. Analyze "As randomized" or "As assigned."	Stats	If IWRS study drug dispense data not match with the treatment label identifier on the Exposure as Collected eCRF page.
Moderate-to-severe patients from etanercept approved countries randomized as severe	Do not exclude from PPS	Monitor and Stats	Either from monitor's list, or If patient with PASI <20 and sPGA <4 at baseline received etanercept in P2.

Important Protocol Deviation Category/Subcategory/Study Specific	Action for PPS Analysis	Source to Identify Protocol Deviation^a	Statistical Programming Guidance for Clinical Study Report

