Subcategory: Compliance	Excluded from PPS	Stats	If non-compliant with study medication regimen or over-dose during the treatment period. Note: Non-compliance with therapy is defined to be missing more than 20% of expected doses and missing 2 or more consecutive doses; over-dose is defined as to take more injections at the same time point than specified in the protocol.
Subcategory: Patient took medication not fit for use	Do not excluded from PPS	Monitor	From monitor's list.
Subcategory: Other			
Randomized but did not take any study medication	Excluded from PPS	Stats	If a patient is randomized but does not take any study medication.
Overdose/ Underdose in terms of actual volume of IP	Excluded from PPS	Monitor	From monitor's list.
Category: Safety			
Subcategory: SAEs			
Failure to report within 24 hours of the PI aware	Do not Excluded from PPS	Monitor	From monitor's list.
Category: Informed Consent			
Subcategory: Informed Consent not Obtained/Missing/Late	Excluded from PPS	Monitor and Stats	Either from monitor's list, or, if patient informed consent date is after Visit 1 date or missing informed consent.
Subcategory: Improper Informed Consent	Do not Excluded from PPS	Monitor	From monitor's list.
Category: Administrative/Oversight			
Subcategory: Reg/Ethic Approvals	Excluded from PPS	Monitor	From monitor's list.
Subcategory: Other			
Enrolled in a site with significant GCP noncompliance issue	Excluded from PPS	Monitor	From monitor's list.

Abbreviations: AE = adverse event; BCG = Bacille de Calmette et Guérin; BSA = body surface area; CDRS-R = Children's Depression Rating Scale–Revised; Con-Meds = concomitant medications; C-SSRS = Columbia–Suicide Severity Rating Scale; DV = protocol deviations; eCRF = electronic case report form; GCP = good clinical practice; IgG = immunoglobulin G; IL = interleukin; ITT = intent-to-treat; IV = intravenous; IWRS = interactive web-response system; PASI = Psoriasis Area and Severity Index; PPD = purified protein derivative; PPS = per protocol set; Ps = psoriasis; PsA = psoriatic arthritis; Reg = regulatory; SAE = serious adverse event; sPGA = static Physician Global Assessment; stats = statistics; TB = tuberculosis; TBL = total bilirubin.

^a The term “Monitor” indicates the protocol deviation will be identified by site monitors and entered into monitor’s list using a spreadsheet. The spreadsheet will be exported as Study Data Tabulation Model (SDTM) DV domain.

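### Subjects who took the wrong study treatment stay in the per-protocol set under their assigned arm, and no Period 2 between-group comparison reflects the drug received

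*SAP*

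**What the plan says.** SAP Section 6.16 calls a subset of the important deviations major: these "are the protocol deviations that might have impact on the efficacy and/or safety results". It defines the PPS as all randomized patients without a major deviation, and uses it to check whether conclusions hold when affected data are left out. Sections 6.6 and 6.11.3 apply the PPS to the co-primary endpoints.

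Table RHCD.6.12 then sets the PPS action for each deviation. For "Took incorrect study medication" the action begins "Do not exclude from PPS. Analyze" and goes on to specify the randomized or assigned treatment. The programming trigger is: "If IWRS study drug dispense data not match with the treatment label identifier on the Exposure as Collected eCRF page". In the same table, "Overdose/ Underdose in terms of actual volume of IP" is an exclusion.

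Table RHCD.6.1 (Section 6.1.1) states for the main-study ITT, the addendum ITT, the PPS and both Period 2 safety populations: "Subjects will be analyzed according to the treatment to which they were assigned". Table RHCD.6.2 names only ITT, PPS and Safety populations for Period 2 comparisons.

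**The concern.** A per-protocol analysis asks whether the result holds among subjects treated broadly as planned. Receiving the other arm's treatment is about as direct a departure from that as there is. If these subjects stay in under their assigned arm, the PPS repeats the ITT classification for exactly this deviation, and the include/exclude check in Section 6.16 cannot test it.

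In safety the usual convention is to group by what the subject took. Here a placebo subject given ixekizumab in error counts as placebo in every Period 2 adverse-event comparison, and an ixekizumab subject given placebo counts as ixekizumab. In the main study, Period 2 is the only placebo-controlled safety comparison, and misclassification in either direction tends to shrink a real difference.

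**Working it through.** **Comparing the rows of Table RHCD.6.12.**

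| Deviation | PPS action |
|---|---|
| Wrong injected volume of study drug | Exclude |
| Prohibited concomitant medication | Exclude |
| Needs another agent effective for psoriasis (D19) | Exclude |
| Earlier etanercept (32) or IL-17 agent (33) | Exclude |
| Randomized, no study drug taken | Exclude |
| Took incorrect study medication | Keep, in assigned arm |

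So a placebo subject with past IL-17 therapy leaves the PPS, while a placebo subject given ixekizumab during Period 2 stays in it as placebo. The SAP gives no reason. Another row, such as compliance or overdose, might remove some of these subjects, but only incidentally.

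**Is any population based on the drug received?** Two are (Table RHCD.6.1):

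- The All Ixekizumab Safety Population takes anyone with at least one ixekizumab dose over Periods 2 to 4. Table RHCD.6.2 gives its comparison as not applicable.
- The Follow-Up Population groups by last treatment received, covers Period 5 only, and has no comparison.

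Neither supplies a Period 2 between-group comparison. Counting and listing deviations (Section 6.16) regroups nobody.

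**Size per subject.** Inputs: arms of 110 and 55 (SAP 5.2.1); addendum arms of 30, 30 and 15 (SAP 5.2.2); response rates of 80% for ixekizumab and 10% for placebo.

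- Largest shift in the main-study placebo rate from one misclassified subject or event: 1/55 = 1.8 points.
- Expected shift in the placebo response rate if that subject responds as if fully treated: (0.80 − 0.10)/55 = 1.3 points.
- Largest shift in the addendum placebo arm, for safety tables only: 1/15 = 6.7 points.

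**Effect on the co-primary tests.** Exact enumeration of the two-sided Fisher test at 0.05, with 110 v 55 and 80% v 10%, gives power above 99.9%, in line with the SAP's >99%. Now assume that m subjects in each arm take the other arm's drug for all of Period 2. The expected difference, in points, is 70 × (1 − m/110 − m/55):

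| m per arm | Expected difference | Power |
|---|---|---|
| 0 | 70.0 | >99.9% |
| 1 | 68.1 | >99.9% |
| 3 | 64.3 | >99.9% |
| 5 | 60.5 | >99.9% |

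These values of m are illustrations; the documents give no error count. The calculation uses the full randomized arms, and the PPS will be somewhat smaller.

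**The case against.** Several points on the other side are sound and limit the concern.

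- **The flag is broader than wrong drug.** It fires on a mismatch between dispensing records and the recorded label. Cartons are assigned by the interactive web-response system (SAP 5.3), so a mismatch may be a different carton of the same treatment. A reader might infer that every flagged subject took the wrong drug; the trigger does not show that. Excluding on the raw flag would remove correctly treated subjects, which is why any exclusion needs confirmation.
- **The action is prespecified.** Major deviations are only a subset of important ones, and the table states its choice openly. That is true, but an explicit choice can still be inconsistent with the stated criterion and the neighbouring rows.
- **Harm is not hidden.** A reader might infer that events after a mistaken ixekizumab dose are lost from the ixekizumab tables. They are not: the All Ixekizumab Safety Population includes that subject, with baseline taken before the first ixekizumab dose (SAP 6.1.2), and adverse events are tabulated for it. What is missing is the comparison.
- **The PPS belongs to the main study.** The 6.7-point figure therefore says nothing about PPS robustness.
- **Mix-ups with etanercept are unlikely.** Etanercept is open label, weekly, has no matching placebo and comes in its own presentations (Addendum 4.1). The addendum efficacy comparison also uses an ITT population, where grouping by assignment is correct, so a loss of power from swaps there is no argument for change.
- **Moving a subject to ixekizumab after one dose would create a new error.** A wrong dose at Week 8 would carry the events of Weeks 0 to 8, which arose on placebo, into the ixekizumab column.
- **The change comes late.** SAP Version 3 followed the primary (Week 12) lock, and that lock held the final Period 2 analysis (SAP 6.17). This affects how added analyses must be labelled, but it does not rule them out: the only revision listed for Version 3 was itself a post hoc change to Table RHCD.6.12.

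**Conclusion.** The concern holds in a limited form. The wrong-treatment row does not fit the purpose that Section 6.16 gives the PPS or the treatment of comparable rows, and no Period 2 between-group comparison reflects the drug received. Grouping by assignment is right for ITT and is not in question.

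The practical size depends on the number of confirmed errors, which the documents do not give. At one subject it is at most 1.8 points in the main-study placebo arm and 6.7 points in the addendum placebo arm, the latter for safety only. This can matter for an uncommon adverse event. A reader might infer that the primary efficacy result is at risk; it is not, since power stays above 99.9% with five full swaps per arm, and in a superiority comparison such errors dilute the effect rather than create one.

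The finding rests on the SAP and the addendum. The main protocol is not among the documents.

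**What to change.** 1. Change the row in Table RHCD.6.12 to exclude from the PPS any subject confirmed to have received at least one Period 2 dose of a treatment other than the one assigned. State that a subject whose mismatch is only another carton of the same treatment stays in.
2. If any confirmed case exists, add a Period 2 safety sensitivity table by treatment received. Keep events before the first wrong dose under the treatment then being received, and state how later events are assigned if the subject returns to the assigned treatment.
3. Leave ITT and the as-assigned safety tables unchanged. Label the revised PPS result and the added table as post hoc.

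If there is no confirmed case, one sentence in the study report closes the point. If the sponsor prefers to keep the current row, the SAP should say why.

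The cost is the possible loss of a few PPS subjects and one extra table. The SAP already compares the dispensing and label data; the added work is confirming, for each flagged subject, which treatment was taken.
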